10.11. Definition of End of Trial

The end of the trial is the date of the last completed 12-month follow-up visit (Visit 2 in section 10.8.3)

11. TRIAL INTERVENTIONS

11.1. Intervention: TAVI with CEP

The device group will have TAVI performed with CEP. The Claret Sentinel dual-filter device (Boston Scientific, MA, USA) is a single use, embolic protection catheter inserted into the right radial or brachial artery. This is the only device currently approved for use in both Europe and the USA, and has the largest body of clinical evidence. The device employs two filters (nitinol frames with 140-micron pores polyurethane film), one delivered to the brachiocephalic artery (Proximal Filter), and one to the left common carotid artery (Distal Filter) before TAVI. Following the TAVI procedure the system is removed.

11.2. Control: TAVI without CEP (standard of care)

The control group will have standard of care as routine for the TAVI without the use of CEP. There is no blinding of the procedure for the operators involved in the trial.

11.3. Discontinuation of the trial treatment

The physician performing the patient's TAVI procedure can discontinue the patient's treatment at any time in accordance with their clinical judgement. These patients will remain in the study and be included in the intention to treat analysis according to the arm to which they were randomised.

11.4. CEP device details

The CEP Claret Sentinel dual-filter device will be provided free of charge to participating hospital sites. To receive the Claret Sentinel dual-filter device the participating hospital must complete standard training and be approved by the company to use the CEP device. Each site will receive 10 devices for training purposes. Provision of devices to sites is covered in the site agreement.

The Claret Sentinel dual-filter device will be used as marketed under its CE mark for this study. Adverse events will be captured as described in section 13.

12. ASSESSING THE QUALITY OF PATIENT INFORMATION IN THE BHF PROTECT-TAVI TRIAL (API STUDY)

12.1. Study design

The API Study is an observational, non-randomised study to assess the quality of information given to BHF PROTECT-TAVI trial participants about the trial prior to consent. Data are collected via a self-administered, paper questionnaire completed by trial participants. The API Study is an optional study open to all BHF PROTECT-TAVI participating sites. The API Study will recruit a maximum of 300 participants. The start and end date of the study will be confirmed by the LSHTM CTU.

12.2. Objectives

- To examine how participants evaluated each source of information they received about the study in understanding the different aspects of trial participation
- To determine which source(s) of information participants found most helpful

12.3. Outcome

Participant-reported perception of BHF PROTECT-TAVI trial information.

12.4. Study participants

At each participating centre, all patients enrolled in the BHF PROTECT-TAVI trial will be considered for the API Study. There are no specific exclusion criteria.

12.4.1. Inclusion criteria

- Patients who have consented to participate in the BHF PROTECT-TAVI trial
- Patients who are willing and able to give informed consent for participation in the API Study

12.4.2. Exclusion criteria

The are no exclusion criteria for the study.

12.5. Screening and eligibility assessment

Patients are approached following their TAVI procedure up to 72 hours post-TAVI or hospital discharge (if sooner).

12.6. Informed consent

BHF PROTECT-TAVI trial participants will be given a copy of the API Study patient information sheet. Written Informed Consent will be obtained by means of a patient dated signature and a dated witness signature of the person who presented the Informed Consent Form. One copy of the signed Informed Consent Form will be given to the participant, one copy will be kept in the local trial site file and the original will be placed in the patient's medical records.

12.7. Data collection

Once consented, participants will be given the paper questionnaire to complete. The questionnaire takes approximately five minutes to complete and is only available in English. Participants' BHF PROTECT-TAVI study ID will be entered on the questionnaire by site staff. This is to allow linkage with demographics data (month and year of birth, gender, ethnicity) collected for the BHF PROTECT-TAVI trial. Participants will also have the option to provide their email address or phone number so they can be contacted by the trial team to discuss their responses.

The completed questionnaires should be scanned by the research staff at the site and emailed to the LSHTM CTU. The electronic copies will be deleted once the questionnaires have been printed. Printed copies will be stored securely in the Clinical Trials Unit at the London School of Hygiene and Tropical Medicine

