10.2. Informed Consent

Only patients who give consent will be included in the trial. If informed consent is not possible, the patient will not be recruited into the trial. Consent will be taken prior to the patient's scheduled TAVI procedure. The patient will be allowed as much time as wished to consider the participant information sheet and the opportunity to question the Investigator, or other independent parties to decide whether to participate in the trial.

If possible, Informed Consent will be obtained in writing by means of a patient dated signature and a dated witness signature of the person who presented the Informed Consent Form.

Oral consent (over the telephone or by videoconference) is also permissible. This will be documented using the approved remote consent form. Baseline data can be collected once consent has been recorded in this manner. However, the participant must personally sign and date the remote consent form to confirm their participation in the trial when they attend hospital. They must sign and date the form before randomisation can take place.

The person who obtained the consent must be suitably qualified and experienced, have been authorised to do so by the Chief/Principal Investigator and authorisation documented on a trial delegation log. One copy of the signed Informed Consent Form will be given to the participant, one copy will be kept in the local trial site file and the original will be placed in the patient's medical records.

For the purposes of informed consent monitoring, redacted consent forms may be requested by the LSHTM CTU and will be sent by secure email.

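### API Study questionnaires carry the study ID and pass openly through site research staff, so courtesy bias may affect the ratings and the comparison of information sources

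*Protocol*

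**What the plan says.** The API Study (protocol section 12) is an optional observational study of at most 300 trial participants. It has two objectives in section 12.2: "To examine how participants evaluated each source of information they received about the study" and "To determine which source(s) of information participants found most helpful". Its single outcome, in section 12.3, is "Participant-reported perception of BHF PROTECT-TAVI trial information".

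The form is on paper and self-administered. It is completed in hospital after TAVI, within 72 hours or before discharge if that is sooner (sections 10.8.1, 12.1 and 12.5). Section 12.7 then fixes how it is handled. On identification: "Participants' BHF PROTECT-TAVI study ID will be entered on the questionnaire by site staff". The reason given is linkage to month and year of birth, gender and ethnicity. On return: "The completed questionnaires should be scanned by the research staff at the site and emailed to the LSHTM CTU". Participants may also choose to leave an email address or phone number so that the trial team can discuss their responses.

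On where the rated information comes from, section 10.2 gives patients the information sheet and "the opportunity to question the Investigator", among others, before they decide. Section 20.4.2 mentions an animated information video.

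**The concern.** The outcome is an opinion, and one plausible object of that opinion is the local team's own explanation of the trial. A participant who knows that the form carries an identifier and goes back through that team has a reason to be polite. The setting adds to this: the participant is still an in-patient, and the local research team will arrange further contact at 6-8 weeks and 12 months (sections 10.8.2 and 10.8.3).

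A courtesy effect that raised all ratings equally would mainly blur the first objective. An unequal effect is more troublesome. There is some reason to spare a person's feelings and less reason to spare a leaflet or a video, so the comparison in the second objective is where harm could arise. If every form follows the same route, the data contain no confidential-return group against which to separate politeness from true preference.

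**Working it through.** The protocol gives no sample-size reasoning, precision target or expected rating for the API Study, so there is no figure of its own to reproduce. The main check is to set the provisions side by side.

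1. **What is measured.** Perception of each source, and which source or sources helped most (sections 12.2 and 12.3). This is subjective and comparative.
2. **Who is among the sources.** The Investigator answers questions and a delegated person takes consent (section 10.2). The information sheet and the video are impersonal sources (sections 10.2 and 20.4.2).
3. **Who handles the identified answers.** Site staff enter the ID, and site research staff scan the completed form and email it before the CTU has it (section 12.7).
4. **What protects the answers from the site.** Self-administration lowers interviewer influence while the form is being filled in, but not afterwards. Section 12.8 protects care on withdrawal and does not deal with candid ratings. Section 12.9 limits access to study staff and authorised personnel, which does not exclude site staff. No sealed or direct return is described.

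Steps 1 to 4 establish an exposure to bias. They do not establish that bias occurs.

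**Illustration only.** This shows how much differential bias would matter at the maximum n = 300. Only the 300 comes from the protocol; the rest is assumed.

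- Precision of one proportion: half-width = 1.96 × √(p(1−p)/300). This gives 5.7 points at p = 50%, 5.2 at 70% and 3.4 at 90%.
- Two sources are truly equal at 70% rated helpful, ratings are independent within a patient, and only the staff rating is inflated, by b. Then p1 = 0.70 + b and p2 = 0.70; the discordant proportion is d = p1(1−p2) + p2(1−p1); and SE = √((d − b²)/300). The chance of wrongly finding staff better is 1 − Φ(1.96 − b/SE).
- Worked case, b = 0.05: d = 0.75 × 0.30 + 0.70 × 0.25 = 0.400; SE = √((0.400 − 0.0025)/300) = 0.0364; b/SE = 1.37; chance = 1 − Φ(0.59) = 28%.

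| Assumed inflation of staff rating | Chance of wrongly favouring staff |
|---|---|
| 0 points | 2.5% |
| 2 points | 8% |
| 5 points | 28% |
| 10 points | 81% |
| 15 points | 99% |

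The table says only that a differential of 5 to 10 points would be enough to mislead. Nothing in the protocol says where on this scale the study lies, and the first row is possible.

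**The case against.** The strongest reply is that much of the mechanism is inferred.

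- The protocol does not say that the person who scans a form informed that patient. The first approach and the information sheet are assigned to the clinical care team (section 10.7), while scanning falls to research staff. Section 10.2 also allows questions to independent parties.
- Staff are told to scan the forms; nothing says that they read them.
- The questionnaire is not shown, so it is not known that staff explanation is a listed item. A patient who wants to please the team might also be generous to its leaflet and video, which would shrink any differential.
- Participants receive a separate API Study information sheet (section 12.6), which is not available here and might tell them who sees their answers.
- The ID has a legitimate purpose, the sub-study is small and optional, and handling at the site allows a check that forms are complete.

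All of this stands as a limit on what can be claimed. A reader might infer that the ratings will be too favourable, that the comparison does tilt towards staff, or that the people rated are the people reading the answers. The protocol supports none of these. It also gives no basis for attaching a size to the bias. What survives is narrower: identified answers pass openly through the local team, that team provides part of the rated information, and section 12 describes no barrier. The reply does not offer a reason to prefer open return beyond speed and the completeness check.

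**Conclusion.** The point holds as a risk. The route in section 12.7 leaves a subjective, comparative outcome open to courtesy bias, which may favour staff explanation over the information sheet or the video. This rests on two assumptions: that staff explanation is among the sources rated, and that participants are aware the site handles their form. Size and direction cannot be determined from the protocol.

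The consequence is small. Only the API Study is affected; no primary, secondary or cost-effectiveness outcome of the main trial depends on it. This is an optional improvement that is worth making because it is cheap.

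**What to change.** Amend section 12.7 as follows.

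- Site staff enter the study ID before handing over the form, so that linkage is kept.
- Optional contact details go on a separate slip.
- The participant seals the completed form and slip in an envelope. It reaches the CTU unopened, either forwarded by the site or posted in a prepaid envelope.
- The CTU does any scanning. The existing sentence on printing and deleting emailed copies would then need adjusting.
- Participants are told, in the API Study information sheet or on the form, that site staff will not see their answers.

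For forms already collected by the present route, report that route as a limitation, particularly when interpreting the comparison of sources.

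The cost is envelopes and postage for at most 300 forms, slightly slower receipt, and the loss of any site check for missing answers. Sites no longer have the scanning task.

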12.8. Participant withdrawal

A participant may decide to withdraw from the API Study at any time and this will not affect their participation in the BHF PROTECT-TAVI trial or the care they receive.

12.9. Confidentiality

The study will comply with the UK General Data Protection Regulation (GDPR) and Data Protection Act 2018. The processing of the personal data of participants will be minimised by making use of a unique participant study number only. All documents will be stored securely and only accessible by study staff and authorised personnel. The study staff will safeguard the privacy of participants' personal data.

Participants have the option to provide their contact details. These will be stored securely in a locked cabinet within a room which is locked in the Clinical Trials Unit at the London School of Hygiene and Tropical Medicine in accordance with UK General Data Protection Regulation (GDPR). The data will not be kept longer than necessary and will be deleted within three months after the end of the BHF PROTECT-TAVI trial.

12.10. Funding

No additional funding is required for the API Study.

12.11. Dissemination

Results will be disseminated through publications, conferences and directly to patients involved in the study.

13. SAFETY REPORTING

13.1. Adverse Event Definitions

Non-Serious Adverse	Any untoward medical occurrence in a participant to whom a medicinal			
Event (NSAE)	product has been administered, including occurrences which are not			
	necessarily caused by or related to that product but which are not			
	considered to be serious as defined below.			
Serious Adverse Event	A serious adverse event is any untoward medical occurrence that:			
(SAE)	results in death			
	is life-threatening			
	 requires inpatient hospitalisation or prolongation of existing 			
	hospitalisation			
	 results in persistent or significant disability/incapacity 			
	 consists of a congenital anomaly or birth defect*. 			
	Other 'important medical events' may also be considered a serious adverse			
	event when, based upon appropriate medical judgement, the event may			
	jeopardise the participant and may require medical or surgical intervention			
	to prevent one of the outcomes listed above.			
	NOTE: The term "life-threatening" in the definition of "serious" refers to an			
	event in which the participant was at risk of death at the time of the event;			
	it does not refer to an event which hypothetically might have caused death			
	if it were more severe.			
Assessment of Causality	The relationship of each adverse event to the trial treatment must be			
	determined by a medically qualified individual according to the following			
	definitions:			
	Probably related: A causal relationship is clinically / biologically highly			
	plausible and there is a plausible time sequence between onset of the			
	adverse event and the treatment			
	Possibly related: A causal relationship is clinically / biologically plausible and			
	there is a plausible time sequence between onset of the adverse event and			
	the treatment			
	Unlikely related: A causal relationship is improbable and another			
	documented cause of the adverse event is most plausible.			
	Unrelated: A causal relationship can definitely be excluded and another			
	documented cause of the adverse event is most plausible.			
Clinical trial activities	Any events that occur as a result of trial specific activities relating to the			
	participant's involvement in the trial. This includes:			
	any complications relating to the CEP device			
	any time delays to treatment or extension of procedural duration			
	any other events that occur as a result of trial specific activities			
	(such as follow-up)			

13.2. Site reporting procedures for Serious Adverse Events to the CTU

The following procedure should be followed by site study teams for the reporting of Serious Adverse Events (SAEs).

- SAEs are reported up to the 6-8-week follow-up timepoint.
 - Expected events are defined as any of the outcomes (see Section 7) or recognised complications of TAVI surgery and CEP use (see Section 13.4). These events should be reported in the eCRF up to discharge and do not need to be reported separately as adverse events. Post-discharge, recognised complications of TAVI surgery and CEP use do not need to be reported.

- Causality will be assessed by the Principal Investigator at each site (as defined in section 13.1).
- Events which, in the opinion of the Principal Investigator, are unrelated to clinical trial activities do not need to be reported.
- Site study teams will report unexpected SAEs (i.e. any not listed in section 7 or 13.4) that are
 possibly, probably or unlikely to be related to clinical trial activities (as defined in section 13.1)
 using the secure, password protected trial database within 7 days of the site study team becoming
 aware of the event.
- The site study team will provide additional, missing or follow up information in a timely fashion as requested.

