10.5. Blinding and code-breaking

Unblinded staff:

This is an open-label trial. Hospital staff will be aware of the allocation of patients.

Blinded trial staff:

As an open-label trial there will be no blinded staff. However, the clinical events committee will be blinded to trial treatment. Supporting documentation sent to the committee will be redacted by staff at the LSHTM CTU.

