13.5. Reporting procedures for Non-Serious Adverse Events

- Events which are expected complications of TAVI surgery and CEP use do not need to be reported separately as adverse events, but should be reported as part of the CRF (see section 13.4)
 - Post-discharge, recognised complications of TAVI surgery and CEP use do not need to be reported.
- Site study team will report unexpected Non-Serious Adverse Events (NSAEs) that are possibly or probably related to clinical trial activities as defined in section 13.1) using the secure, password protected trial database within 14 days of the site study team becoming aware of the event.
- NSAEs are reported up to the 6-8-week follow-up timepoint.
- The site study team will provide additional, missing or follow up information in a timely fashion if requested.
- The Chief Investigator will review reported AEs for causality as defined in section 13.1.

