17.2. Data Monitoring Committee (DMC)

17.2.1. Role of the DMC

The DMC examine the data accumulated during progress of the BHF PROTECT-TAVI trial and ensure that the benefit/risk balance remains acceptable for participating patients. It is the only committee which will have access to data broken down by treatment during the trial and on this basis, the primary responsibility of the DMC is to review interim analyses of outcome data and to recommend to the Trial Steering Committee (TSC) whether the trial needs to be changed or terminated based on these analyses.

More specifically, the duties of the DMC will include:

- 1) monitoring evidence for treatment differences in the primary and secondary outcomes
- 2) monitoring evidence for treatment harm (e.g. deaths, adverse events)
- 3) assessing the impact and relevance of external evidence
- 4) deciding whether to recommend that the trial continues to recruit participants or whether recruitment should be terminated either for everyone or for some treatment groups and/or some participant subgroups
- 5) assessing data quality, including completeness

- 6) reviewing recruitment figures and monitor losses to follow-up
- 7) monitoring compliance with the protocol by participants and investigators
- 8) monitoring continuing suitability of patient information
- 9) monitoring compliance with previous DMC recommendations

The DMC will meet as required.

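### Unexpected adverse events pass through an unblinded causality filter built mainly on the CEP device, so their counts are not a valid between-arm measure of harm

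*Protocol*

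**What the plan says.** All references are to the Protocol.

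- **Serious events (13.2).** The site Principal Investigator assesses causality. Unexpected SAEs are reportable if "possibly, probably or unlikely to be related to clinical trial activities (as defined in section 13.1"). The remaining category is dropped: "Events which, in the opinion of the Principal Investigator, are unrelated to clinical trial activities do not need to be reported".
- **Non-serious events (13.5).** The rule is narrower: "Site study team will report unexpected Non-Serious Adverse Events (NSAEs) that are possibly or probably related to clinical trial activities". The Chief Investigator then reviews causality, but only for events already reported.
- **What counts as a trial activity (13.1).** Three items are listed: "any complications relating to the CEP device"; "any time delays to treatment or extension of procedural duration"; and other events caused by trial-specific activities, with follow-up as the example.
- **What counts as unrelated (13.1).** "Unrelated: A causal relationship can definitely be excluded and another" documented cause must be the most plausible one.
- **Who knows the allocation (10.5).** "Hospital staff will be aware of the allocation of patients".
- **Use of the data (17.2.1).** The DMC alone sees data by arm, and its duties include "monitoring evidence for treatment harm (e.g. deaths, adverse events").
- **Events outside the filter (13.2, 13.4, 10.8).** Section 7 outcomes and the listed TAVI and CEP complications go into the eCRF up to discharge with no causality condition. Mortality and vascular injury are collected again at 6-8 weeks, and mortality at 12 months.

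**The concern.** The reporting rule asks whether an event is related to something that, in the main, only one arm receives. Control participants have routine TAVI (11.2). No device complication is possible for them, and little in their care is specific to the trial.

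The same unlisted event can then be kept in one arm and dropped in the other. Take a serious seizure on day 4. It is not on the 13.4 lists and falls after the 72-hour outcome window. In a CEP participant the investigator can seldom exclude the device with certainty, so the event is reported. In a control participant the device is excluded automatically, and the event can be rated unrelated and never recorded.

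Unlisted events are where an unforeseen harm of the device would appear. If they are counted differently by arm, a false excess could arise with CEP, or a true excess could be put down to reporting. No analysis can recover events that were never collected, and the central causality review sees only what sites have sent.

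**Working it through.** **1. Which events pass the filter**

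| Event type | Recorded if | Depends on causality? |
|---|---|---|
| Death, stroke and other section 7 outcomes | they occur, at the scheduled times | No |
| Vascular complications | they occur, at 72 hours or discharge and at 6-8 weeks | No |
| Other 13.4 complications | they occur, up to discharge | No |
| Unexpected SAE, to 6-8 weeks | rated unlikely, possibly or probably related | Yes |
| Unexpected NSAE, to 6-8 weeks | rated possibly or probably related | Yes, more strictly |

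Only the last two rows are in question.

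**2. What each arm is exposed to under the 13.1 definition**

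| Activity | CEP arm | Control arm |
|---|---|---|
| Device complication | Yes | No |
| Delay or longer procedure | Yes (10.7 says CEP adds about 5 minutes) | Little, if any |
| Other trial-specific acts, such as follow-up | Yes | Yes |

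**3. The causality reference differs between sections.** Section 13.1 defines the categories by relationship to the trial treatment. Sections 13.2 and 13.5 apply them to clinical trial activities. One site could treat a control participant's TAVI as the trial treatment and report; another could treat it as routine care and not report.

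**4. Size.** The protocol states no rate of unexpected events and no reporting share, so there is no plan figure to reproduce. Its only input here is the sample size: 9712 randomised 1:1 gives 9712 / 2 = 4856 per arm.

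Let *r* be the true rate of unexpected SAEs, equal in both arms, and *a* and *b* the shares reported under CEP and control. Expected reports are 4856·*r*·*a* and 4856·*r*·*b*. The ratio is *a*/*b*, whatever the value of *r*. The values of *r*, *a* and *b* below are assumptions.

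| *r* | *a* v *b* | Reports, CEP v control | Ratio | Chance of p<0.05 |
|---|---|---|---|---|
| 1% | 80% v 50% | 38.8 v 24.3 | 1.6 | 45% |
| 2% | 80% v 50% | 77.7 v 48.6 | 1.6 | 74% |
| 5% | 80% v 50% | 194.2 v 121.4 | 1.6 | 99% |
| 2% | 50% v 10% | 48.6 v 9.7 | 5.0 | >99% |
| 2% | 30% v 5% | 29.1 v 4.9 | 6.0 | 99% |

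The last column is the probability that a two-sided 5% comparison of two proportions is significant when there is no true difference. For the second row the reported proportions are 0.02 × 0.80 = 0.016 and 0.02 × 0.50 = 0.010, with pooled value 0.013:

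- null SE = √(2 × 0.013 × 0.987 / 4856) = 0.00230, and 1.96 × 0.00230 = 0.00451
- alternative SE = √((0.016 × 0.984 + 0.010 × 0.990) / 4856) = 0.00230
- z = (0.006 − 0.00451) / 0.00230 = 0.65, so the probability is 0.74

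If *a* = *b* the ratio is 1.0. About 78 v 49 reports would look the same under equal reporting with a true ratio of 1.6 as under no true difference with 80% v 50% reported. The counts alone cannot separate the two.

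**The case against.** **The SAE filter is weak.** A reader might infer that SAEs are reported only when the investigator links them to the trial. That is true of NSAEs but not of SAEs. SAEs rated unlikely to be related are reportable, and the unrelated category requires both definite exclusion and another documented cause. Read literally, a control SAE with no documented cause could not be rated unrelated. This narrows the gap but does not close it: where another cause is documented, exclusion is easy for a participant who never had the device and hard for one who did.

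**The main harms are collected evenly.** A reader might infer that the DMC's harm monitoring as a whole is compromised. The protocol does not support that. Death, stroke, and the 34 TAVI and three CEP entries in 13.4, which include bleeding, infection, kidney injury, dissection and vascular injury, carry no causality condition. They cover the vascular injury, infection and bleeding that 20.4.3 names as CEP risks. This stands in full for the in-hospital period. After discharge the listed complications need not be reported in either arm, so apart from section 7 outcomes the filtered stream is then the only site adverse event reporting.

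**No comparison of filtered counts is promised.** Section 17.2.1 mentions adverse events only as an example, and the DMC charter and SAP, which are not shown, may settle what is compared. That is fair as to analysis. The collection rule and its inconsistent reference, however, are fixed in the protocol, and no later document can restore unrecorded events.

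**It was a deliberate choice.** Version 3.0 limited SAE reporting by relatedness (Appendix B), for a device used as marketed under its CE mark. That is a reasonable basis for reducing site burden and for expedited reporting. It does not make the resulting counts comparable by arm.

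**Conclusion.** The point holds for unexpected adverse events up to 6-8 weeks, and only for those. Whether such an event is recorded depends on a judgement made with knowledge of the allocation, against a reference that applies mainly to the CEP arm. The likely direction is excess reporting with CEP. The effect should be more marked for NSAEs, where a positive link is needed, than for SAEs.

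The size cannot be established from the protocol. Under the assumed shares the spurious ratio is 1.6 to 6.0. It depends wholly on those shares, and the range should be read as an illustration, not an estimate.

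The comparison of deaths, section 7 outcomes, vascular complications and 13.4 complications up to discharge is unaffected. It would be wrong to conclude that no safety signal or reassurance from this trial could be trusted.

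**What to change.** **Wording in 13.2, 13.5 and 17.2.1.** State that:

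- between-arm safety comparisons, for the DMC and the final report, use only events recorded in both arms regardless of causality: deaths, section 7 outcomes including vascular complications to 6-8 weeks, and 13.4 complications entered in the eCRF up to discharge;
- unexpected SAEs and NSAEs that have passed the causality filter are shown as listings and are not compared between arms.

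**Causality reference.** Use one reference in 13.1, 13.2 and 13.5, and say how it applies to a control participant, so that sites apply it in the same way in both arms.

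**Cost.** This is wording only, with no new data collection. The price is that unlisted events have no between-arm comparison. Readmissions by arm from the planned HES linkage (14.6, 14.7) could partly fill the gap, but only for participants at NHS sites and with delay, so they would be of limited use to the DMC.

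Removing the filter for unexpected SAEs in both arms, and keeping relatedness for expedited reporting, would deal with the cause. At this stage it would add site work and capture mainly later participants, so it is an option to weigh and not part of the recommended change.
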